6.2. Exclusion Criteria

- Patients with known history of serious allergic reactions, including anaphylaxis, to Zilucoplan® or inability to receive antibiotic prophylaxis due to allergy to ALL of the antibiotics that can be given for prophylaxis of meningococcal disease
- History of active or past meningococcal disease
- Invasive mechanical ventilation > 24 h at randomization**
- Patient on ECMO at screening
- Clinical frailty scale above 3 before onset of the COVID-19 episode
- Weight below 54 kg as measured max 1 week prior to inclusion
- Weight above 150 kg as measured max 1 week prior to inclusion
- Active bacterial or fungal infection
- Unlikely to survive beyond 48h
- Neutrophil count below 1500 cells/microliter
- Platelets below 50.000/microliter
- Patients enrolled in another investigational drug study
- Patients on high dose systemic steroids (> 8 mg methylprednisolone or equivalent for more than 1 month) or other moderately immunosuppressive drugs (in the opinion of the investigator) for COVID-19 unrelated disorder
- Patients on current complement inhibiting drugs
- Serum transaminase levels >5 times upper limit of normal, unless there are clear signs of cytokine release syndrome defined by LDH >300 IU/L and ferritin >700 ng/ml
- Pregnant or breastfeeding females (all female subjects deemed of childbearing potential by the investigator must have negative pregnancy test at screening)

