13.2. Reporting requirements

13.2.1. AE reporting

AE's will be recorded from the first drug administration until the end of the study, as defined in section 5.2.

Special attention will be given to those subjects who have discontinued the study for an AE, or who experienced a severe or a serious AE. All AE's should be recorded in the patient's file and in the CRF.

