10.2 Adverse events

An AE is any untoward medical occurrence in a participant or clinical investigation participant administered a pharmaceutical product that does not necessarily have a causal relationship with this treatment. An AE can therefore be any unfavorable and unintended sign (including an abnormal laboratory finding), symptom, or disease temporally associated with the use of a medicinal (investigational) product, whether or not related to the medicinal (investigational) product.

AEs are further characterised as pre-treatment or treatment emergent.

A pre-treatment AE are events whose onset date and time is prior to the first administration of study drug (Zilucoplan® for Arm A and IV antibiotic for Arm B).

A TEAE is defined as any AE with a start date/time on or after the first dose of study treatment up until the D28 visit. Any AE with an onset date later than the D28 visit for a participant will not be considered as treatment-emergent and therefore will not be included in the tabulations of TEAEs. Where dates are missing or partially missing, AEs will be assumed to be treatment-emergent, unless there is clear evidence to suggest that the AE started prior to the first dose of study treatment. Missing or partially missing dates for AEs will be handled as described in [Section 4.2.3](#). All AEs for a participant will be recorded in the eCRF from the time of informed consent until completion or early study discontinuation.

For each AE the following information should be provided in the eCRF: AE term (verbatim), date and time of onset, whether or not the AE was classified as an SAE, relationship to study treatment, severity, action taken with study treatment, other action taken, outcome, date and time of outcome and whether the AE led to study treatment discontinuation or to study discontinuation.

COVID-19 infection is a very recent syndrome, on which few data are available. Therefore, normal symptoms and natural disease course symptoms that will not be reported as adverse events are dyspnea, coughing, malaise, fever, drop in oxygen saturation, progression to respiratory failure, progression to ARDS, drop in blood pressure. However, progression to multi-organ failure may have other etiologies and will be reported as an SAE.

The number and percentage of participants who experience TEAEs will be summarized by MedDRA preferred term (PT) and treatment.

Summaries of TEAEs may include the following:

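### SAP 10.2 defines treatment-emergent AEs by start date alone, so an AE with pre-dose onset that worsens after dosing is left out of its by-arm TEAE tables

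*SAP*

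**What the plan says.** SAP 10.2 uses two classes: "AEs are further characterised as pre-treatment or treatment emergent". The first is defined by onset: "A pre-treatment AE are events whose onset date and time is prior to the first administration of study drug", meaning zilucoplan in Arm A and the IV antibiotic in Arm B. So is the second: "A TEAE is defined as any AE with a start date/time on or after the first dose of study treatment", with the window closing at the D28 visit. Nothing is said about an event that starts before the first dose and gets worse after it.

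The by-arm summaries that SAP 10.2 goes on to list are all of TEAEs. They comprise an overview (any, serious, severe, related and fatal TEAEs, and those leading to discontinuation), then incidence by preferred term, by maximum intensity, by maximum CTCAE grade and by closest relationship. The listings are wider: all AEs, all serious AEs and discontinuations due to AEs are listed by participant and treatment, whatever the onset.

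SAP 2.2.4.1 gives the key safety endpoints as the number of AEs and SAEs and the severity of AEs, from first dose on D1 to D28.

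The documents differ on when recording starts. The SAP says: "All AEs for a participant will be recorded in the eCRF from the time of informed consent until completion or early study discontinuation". Protocol 13.2.1 says AEs "will be recorded from the first drug administration until the end of the study".

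**The concern.** An adverse drug effect can appear as the worsening of something that has already begun. Under an onset-only rule, that worsening belongs to a pre-treatment event and adds nothing to the by-arm TEAE counts, even if it reaches a severe grade within the window that the key safety endpoint covers.

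The default also runs against the caution shown elsewhere in SAP 10.2. There, an AE with a missing date is presumed treatment-emergent, a missing relationship is counted as related, and a missing intensity is counted as severe. For worsening, the doubt is resolved the other way.

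At stake is the by-arm answer to the protocol's safety objective, which is stated as the number of AEs and SAEs.

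**Working it through.** No figure in the plan needs reproducing. The check traces one case through the planned outputs: an AE that starts after consent and before the first dose, keeps that onset date in the eCRF, and worsens after dosing.

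| Course after first dose | SAP 10.2 by-arm TEAE tables | Where it does appear |
|---|---|---|
| Higher grade, not serious, treatment continues | Absent | Listing of all AEs only |
| Higher grade, treatment stopped for it | Absent | Listings of all AEs and of discontinuations due to AEs; by-arm disposition table (SAP 5.1) |
| Becomes serious | Absent | Listing of all serious AEs; perhaps the Interim 2 SAE summary |
| Fatal | Absent from the row for TEAEs leading to death | Deaths by arm in disposition (SAP 5.1); all-cause mortality by arm at D28 and at follow-up (SAP Table 8.1), in neither case tied to the AE |

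Interim 2 is marked as uncertain because the outline in SAP 2 names SAE incidence by arm separately from TEAE incidence, while SAP 4.4.2 says AEs will be presented as in SAP 10.2, where every table is a TEAE table.

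**Dependence on data entry.** The same clinical course can be counted in two ways:

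- The site keeps one record with its original onset: it counts 0 in the TEAE tables.
- The site opens a new record dated at the worsening: it counts 1.

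Neither document says which to do. A site that follows Protocol 13.2.1 may also never record the pre-dose phase, so the onset date it enters is not determined. The trial is open-label, so the arm is known when the record is made.

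**Length of the exposed window.**

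- Consent to randomisation: at most 24 h (SAP 2).
- Randomisation to first dose: very soon after (SAP 2) or about 24 h (SAP 2.2.1.2).
- Longest total: 24 + about 24 = about 48 h.

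**Weight of one case.** With the planned 54 and 27 participants, one omitted participant changes an incidence by 1/54 = 1.9 percentage points in Arm A or 1/27 = 3.7 in Arm B. How many such cases to expect cannot be derived: neither document gives a rate of pre-dose AEs or of their worsening.

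**The case against.** The strongest reply is that little falls through. The exposed window is at most about two days. A site that follows Protocol 13.2.1 records almost nothing before the first dose. Dyspnoea, fever, desaturation, respiratory failure, ARDS and a fall in blood pressure, which are likely to start and worsen in those days, are not reported as AEs at all (Protocol 13.5, SAP 10.2). SAP 10.2 also foresees several records of one event, since it takes the maximum intensity over repeats, and eCRF completion guidance outside these documents may already require a new record on worsening. SAE reporting under Protocol 13.2.2 covers the whole study period and does not use the TEAE rule. All of this stands and limits the size of the problem. None of it supplies the missing clause.

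Two stronger readings are tempting, and the documents do not support either.

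- A reader might infer that such an event reaches no by-arm output at all, even when serious or fatal. The table above shows otherwise: deaths and treatment stopped for an AE are counted by arm, and SAEs are listed by treatment and may be summarised at Interim 2. The omission is complete only for a non-serious worsening that does not stop treatment.
- A reader might infer that the rule hides worsening of the abnormalities required or allowed at entry, such as the exclusion "Serum transaminase levels >5 times upper limit of normal, unless there are clear signs of cytokine release syndrome". These findings are generally present before consent, so they are baseline findings rather than pre-treatment AEs. Their worsening after dosing can be a new AE with a post-dose start, and so a TEAE. They are lost only if a site enters the AE with the earlier onset.

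**Conclusion.** The point holds in a limited form. The rule in SAP 10.2 gives the wrong class to an AE with a recorded pre-dose onset that increases in grade or becomes serious after the first dose, and so leaves it out of every by-arm TEAE table in that section. This does not fit the SAP's own endpoint of AE severity from first dose to D28.

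The conclusion assumes that the event keeps its pre-dose onset in the eCRF. The number of participants affected is probably small, and any specific count would be a guess. The case for acting is that the arms are small, so one or two events can be visible in a by-arm comparison, and that the correction is cheap. It does not touch the efficacy analyses.

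**What to change.** In SAP 10.2, extend the TEAE definition to include an AE with onset before the first dose that increases in CTCAE grade or becomes serious on or after the first dose, up to the D28 visit. In support of this:

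- Instruct sites to enter such a worsening as a new AE record dated at the worsening.
- At data review, go through the existing AEs with pre-dose onset and flag those that worsened.
- Reconcile the start of AE recording between Protocol 13.2.1 (first drug administration) and SAP 10.2 (consent).
- State whether the Interim 2 SAE summary covers all SAEs or only treatment-emergent ones.

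The cost is one clause in the SAP, one line of recording guidance, the reconciliation of the two recording rules, and a review of what should be few records. The downside is that TEAE counts may rise slightly in both arms.

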3.2. Secondary Objectives

- to study if early intervention with Zilucoplan® is safe (number of AEs/SAEs)
- to study if early intervention with Zilucoplan® affects clinical outcome defined by duration of hospital stay, 6-point ordinal scale, time to defervescence, supplemental oxygen use and SOFA score
- to study if early intervention with Zilucoplan® affects progression to mechanical ventilation and/or ARDS and duration of ICU stay
- to study if early intervention with Zilucoplan® affects the rate of nosocomial infection
- to study if treatment with Zilucoplan® has a favourable effect on long term at follow up 12-22 weeks post-randomization
- to study if treatment with Zilucoplan® affects all-cause mortality rate at day 28 and at 12-22 weeks post-randomization

4. End Points + Time Points

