2.2.4 Safety endpoint(s)

2.2.4.1 Key safety endpoint(s)

The key safety endpoints of this study are the incidence/number of adverse events (AE), serious adverse events (SAE) and the severity of AEs from first dose of study treatment on D1 until D28. Each AE will be categorized as a Treatment Emergent Adverse Event (TEAE) or not. All cases will be assessed by the reporting medically qualified professional or Sponsor as to having a reasonable suspected causal relationship to study treatment or not and categorized on the eCRF as

1. Not related
2. Unlikely
3. Possible
4. Probable
5. Definitely

All AE/SAEs that fall into the last 3 categories are deemed as related to study treatment and will be classified as an Adverse Reaction (AR) or Serious Adverse Reaction (SAR) respectively.

Each SAEs will also assessed as to whether it was an unexpected SAR (Suspected Unexpected Serious Adverse Event, SUSAR)

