3.2.1.3 Nominal Days

The pre-specified protocol nominal days are labelled as follows:

- Day -1
- D1
- D2

- D6
- D15
- D28
- Follow-up

The study protocol specifies that clinical and laboratory parameters be collected as frequently as possible, which would be daily. A window of +/- 1 relative day for each specified nominal day after D2 (+ 1 day for D2) will be allowed if a measurement was not collected on the specified relative day. The window for D28 is +/- 3 days. If a large proportion of data fall outside this window, then increasing the window to +/-2 days for nominal D6, nominal D15 and D28 will be considered.

An additional indicator variable will be derived, DISCHARGE DAY (Y/N), which will identify the relative day that the participants was discharged from hospital. If discharge is on or earlier than relative day 6, between relative day 7 and relative day 15 inclusive or between relative day 16 and relative day 28 inclusive, an additional row mapping the results of the discharge visit to nominal D6, or nominal D15 and nominal D28 respectively. For the primary endpoints a LOCF approach will be utilized for the participants who discharge i.e. if a participant discharges at Day 4 then that oxygenation measure will be mapped to Day 6, Day 15 and Day 28. The approach may be extended to secondary parameters. Data from participants who leave hospital for reasons other than clinical improvement will not be mapped to the nominal days as described above. Participants who die whilst in hospital are not considered as ‘discharged’. Separate indicator variables will be derived to indicate whether a participant has died on a specific relative day and if treatment was discontinued due to an adverse event.

The Nominal Day variable with the above labels will be derived from the relative days and allowable window for all collected endpoints. Since the ideal is to take measurements as frequently as possible, some measurements of some endpoints will not have a Nominal Day associated with them. When these values (without an associated Nominal Day) are to be summarized, graphed or analysed in statistical models, Relative Day will be used as either a continuous variable or categorical as defined in the respective sections. Nominal Day will only ever be used as a categorical variable.

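### SAP 10.2 tabulates AEs by arm only up to each participant's D28 contact, so non-fatal AEs and SAEs recorded from then to week 12-22 get no count by arm

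*SAP*

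**What the plan says.** **The window.** SAP 10.2 defines a treatment-emergent AE (TEAE) as one starting "on or after the first dose of study treatment up until the D28 visit". It continues: "Any AE with an onset date later than the D28 visit for a participant will not be considered as treatment-emergent", and such an event "therefore will not be included in the tabulations of TEAEs". The six summaries that follow (overview, incidence, intensity, CTCAE grade, relationship, non-serious events above 5%) are all summaries of TEAEs.

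**The recording period.** In the same section, AEs "will be recorded in the eCRF from the time of informed consent until completion or early study discontinuation". Protocol 13.2.1 says they "will be recorded from the first drug administration until the end of the study", which Protocol 5.2.1 places, for an individual, at the week 12-22 visit. Protocol 13.2.2 requires SAEs to be reported over the entire study.

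**The objective.** Protocol 3.2 gives the safety objective as "to study if early intervention with Zilucoplan® is safe (number of AEs/SAEs", and Protocol 4.2 repeats it as an endpoint. Neither sets a day limit. SAP 2.2.4.1 introduces one: its key safety endpoints run "from first dose of study treatment on D1 until D28".

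**The D28 contact.** Protocol 9.2 places it at day 28 post-randomisation or within the next 3 days. It is a phone call, or takes place in hospital if the participant is still admitted (SAP 3.2.1.2). SAP 3.2.1.2 also fixes the end of the primary assessment period at 28 days post-randomisation for every participant.

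**The concern.** The trial collects AEs and SAEs for up to 22 weeks, but its planned AE tables stop at about four. SAP 10.2 divides AEs into pre-treatment and treatment-emergent, and an event after D28 is neither. It reaches the participant listings of all AEs and all serious AEs and goes no further: no number of participants, no percentage and no event count by arm. The final analysis, made after follow-up, would therefore add no later-onset event to the AE tables available when all participants have passed D28.

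At stake is whether the report can summarise the safety objective over the period in which the data were collected. In an open-label phase 2a trial with 54 and 27 participants, a reader should not have to build that comparison by hand from listings.

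A second, smaller matter is how the window ends. Section 10.2 ties it to an attended contact and not to a date. The end therefore moves with the contact, and the section does not say what applies if the contact does not take place.

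**Working it through.** The plan states no figure for this point, so there is none to reproduce. The check compares the periods and does the day arithmetic.

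**1. Days recorded but not tabulated**

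Inputs: follow-up at 12 to 22 weeks; cut-off at day 28. I take recording to end at each participant's own follow-up visit, which is how SAP 10.2 puts it.

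- 12 weeks × 7 = day 84; 22 weeks × 7 = day 154.
- Visit at week 12: 84 − 28 = 56 days; 56/84 = 66.7%.
- Visit at week 22: 154 − 28 = 126 days; 126/154 = 81.8%.
- If the contact falls on day 31, the latest the protocol allows: 84 − 31 = 53 days (63.1%) and 154 − 31 = 123 days (79.9%).

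These are shares of calendar time, not of events.

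**2. What that could mean in participants**

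The documents give no risk of a non-fatal SAE after D28. For assumed risks of 2%, 5% and 10%, the expected numbers of participants with a late SAE outside the tables are:

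| Assumed risk | Arm A (54) | Arm B (27) |
|---|---|---|
| 2% | 1.1 | 0.5 |
| 5% | 2.7 | 1.4 |
| 10% | 5.4 | 2.7 |

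**3. Which late events are counted by arm somewhere**

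- Deaths: yes. SAP 5.1 counts participants who died, by arm and with no D28 limit. SAP Table 8.1 models mortality at 12-22 weeks by arm, with percentages, an odds ratio and confidence intervals. Protocol 11.2 adds a survival analysis from Day 1 to the end of follow-up.
- Nosocomial infection: only within the 28-day assessment period.
- Other non-fatal AEs and SAEs: listings only.

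**4. How far the cut-off moves**

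Under Protocol 9.2 the contact falls on day 28 to 31, a spread of 3 days; 3/28 = 10.7% of the window. SAP 5.1 foresees participants who finish treatment but do not complete D28 procedures. Section 10.2 has no rule for them; its rule on missing dates concerns AE dates, not a missing contact.

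**5. Is a 28-day window reasonable?**

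Protocol 8.1.8 gives at most 14 days of C5 inhibition on treatment, then at most 14 days after dosing: 14 + 14 = 28. The horizon matches the period of stated drug effect.

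**6. Which fixed date can serve**

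SAP 3.2.1.1 counts relative day from the first dose during dosing, but from the last dose afterwards. Relative Day 28 after a last dose on day 14 would be day 14 + 28 = 42. For Arm B, if study treatment is taken to be the 7-day antibiotic course, it would be day 7 + 28 = 35. That is not a common cut-off. The date in SAP 3.2.1.2, 28 days post-randomisation, is.

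**The case against.** **The 28-day limit is prespecified and reasoned.** This stands. It is stated as the key safety endpoint in SAP 2.2.4.1, it agrees with the pharmacology in Protocol 8.1.8, and Protocol 4.2 and 4.3 use the same horizon for nosocomial infection and for SARs and SUSARs. A reader might infer that the TEAE definition is wrong; the documents do not support that. Nor is it a clear undeclared change that SAP 3.8 fails to list: Protocol 11.2 promises a summary of secondary endpoints but specifies no AE window.

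**Late events are not hidden.** This also stands. The listings of all AEs and all serious AEs have no D28 limit and show treatment, onset, intensity and relationship. With 81 participants, counts could be compiled from them. A reader might infer that late SAEs escape any comparison by arm. That is too strong, because death is an SAE and deaths are compared by arm to the end of follow-up. What remains is that no count of the non-fatal events is planned.

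**The summary list is permissive and the table shells are a separate document.** True: 10.2 says what the summaries may include. But the exclusion of later events from the tabulations is a stated rule, and shells that follow the SAP would follow it.

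**The moving cut-off is trivial.** Largely true of its size. SAP 3.2.1.3 says "The window for D28 is +/- 3 days", from which a reader might infer windows running from day 25 to day 31. That rule assigns measurements to nominal days; it does not schedule the contact, which the protocol never places before day 28. One might also infer that a participant who misses the contact has all events to week 22 counted as treatment-emergent, a window of 154/28 = 5.5 times the intended length. That needs a missed contact, a visit at week 22, and an analyst who ignores the fixed D28 in SAP 2.2.4.1 and 3.2.1.2. The documents give no rate of missed contacts. This is a gap in wording, not a demonstrated distortion.

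**Conclusion.** The point holds in a limited form. SAP 10.2 leaves non-fatal AEs and SAEs after D28 without a by-arm summary, although the trial records them and its AE/SAE objective has no day limit. The gap covers 67% to 82% of recorded calendar time, assuming a D28 cut-off and recording to each participant's own follow-up visit. How many events that leaves out cannot be said from the documents.

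The 28-day TEAE window should stay. The fault in it is narrower: its end depends on the date of the contact, a shift of up to 3 days, with no fallback if the contact is missed, when a fixed date already stands elsewhere in the SAP. No primary result, sample size or power figure is affected. The point bears on how completely a secondary safety objective is reported, and the repair is cheap enough to be worth making.

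**What to change.** 1. In SAP 10.2, end the TEAE window at 28 days post-randomisation, the date in SAP 3.2.1.2, for every participant, whether or not the D28 contact took place. Do not word it as relative Day 28, which SAP 3.2.1.1 recounts from the last dose.
2. Keep the 28-day TEAE tables as the main AE presentation.
3. Add one by-arm descriptive table of all AEs and SAEs with onset from first dose to the follow-up visit. Show participants with at least one event, number of events, and events per person-time, because follow-up varies from 12 to 22 weeks. Add a footnote that late events are less likely to be drug-related.
4. While editing, reconcile the start of AE recording: informed consent in SAP 10.2, first drug administration in Protocol 13.2.1. The added table starts at first dose and does not depend on this.

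The cost is a few sentences in the SAP and one extra table from data already collected. The downside is that the long-window table mixes drug effect with the later course of the illness, which is why it should be descriptive and secondary to the 28-day tables.
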